3.2 Exclusion Criteria

Patients who meet any of the following criteria will be excluded from study entry.

1. Evidence of locally advanced or metastatic bladder cancer (including current disease involving renal pelvis, ureter, or prostatic urethra).
2. Evidence of muscle-invasive bladder cancer
3. Evidence of extravesical bladder cancer
4. Active central nervous system (CNS) metastases.
5. Prior treatment with PD-L1 or PD-1 inhibitor.
6. Prior radiation to bladder
7. Patient has a known additional malignancy that required active treatment within the last 2 years. Exceptions include basal cell carcinoma of the skin or squamous cell carcinoma of the skin.
8. Patient is considered a poor medical risk that would interfere with cooperation with the requirements of the study.
9. Patient has a condition or laboratory abnormality that might confound the study results, or interfere with the patient's participation for the full duration of the study treatment.
10. Patient has not recovered (i.e. to \leq Grade 1 or to baseline) from previous intravesical BCG or other anti-cancer therapy induced AEs.
 - alopecia, sensory neuropathy Grade ≤ 2 , or other Grade ≤ 2 not constituting a safety risk based on investigator's judgment are acceptable
11. Treatment with any approved anti-cancer therapy, including chemotherapy (systemic or intravesical), radiation therapy, or hormonal therapy within 3 weeks prior to the first dose of study treatment
 - Use of hormone-replacement therapy and oral contraceptives is permitted.
12. Treatment with any other investigational agent or participation in another clinical study with therapeutic intent within 4 weeks prior to the first dose of study treatment
13. Pregnant or lactating, or intending to become pregnant during the study
 - Women who are not postmenopausal (≥ 12 months of non-therapy-induced amenorrhea) or surgically sterile must have a negative serum pregnancy test result within 14 days prior to the first dose of study treatment.

14. History of severe allergic, anaphylactic, or other hypersensitivity reactions to chimeric or humanized antibodies or fusion proteins
15. Known hypersensitivity to biopharmaceuticals produced in Chinese hamster ovary cells
16. Allergy or hypersensitivity to components of the avelumab formulation
17. History of autoimmune disease, including but not limited to myasthenia gravis, myositis, autoimmune hepatitis, systemic lupus erythematosus, rheumatoid arthritis, inflammatory bowel disease, vascular thrombosis associated with anti-phospholipid syndrome, Wegener's granulomatosis, Sjögren's syndrome, Guillain-Barré syndrome, multiple sclerosis, vasculitis, or glomerulonephritis
 - Patients with medically controlled endocrinopathy (e.g., hypothyroidism, adrenal insufficiency), diabetes type I, vitiligo, psoriasis, or hypo- or hyperthyroid diseases not requiring immunosuppressive treatment are eligible
18. Prior allogeneic stem cell or solid organ transplantation
19. Current use of immunosuppressive medication, EXCEPT for the following: a. intranasal, inhaled, topical steroids, or local steroid injection (e.g., intra-articular injection); b. Systemic corticosteroids at physiologic doses \leq 10 mg/day of prednisone or equivalent; c. Steroids as premedication for hypersensitivity reactions (e.g., CT scan premedication).
20. History of idiopathic pulmonary fibrosis, organizing pneumonia (e.g., bronchiolitis obliterans), drug-induced pneumonitis, idiopathic pneumonitis, or evidence of active pneumonitis on screening chest CT scan
 - History of radiation pneumonitis in the radiation field (fibrosis) is permitted.
21. Positive test for HIV
22. Active hepatitis B (positive hepatitis B surface antigen [HBsAg] test at screening);
 - Patients with past or resolved hepatitis B (HBV) infection (positive anti-hepatitis B core antigen [anti-HBc] antibody test) are eligible. HBV DNA must be obtained in these patients prior to the first dose of study treatment.
23. Active hepatitis C
 - Patients positive for hepatitis C virus (HCV) antibody are eligible only if polymerase chain reaction assay is negative for HCV RNA.
24. Active infection requiring systemic therapy
25. Severe infections within 4 weeks prior to the first dose of study treatment, including but not limited to hospitalization for complications of infection, bacteremia, or severe pneumonia
26. Significant cardiovascular disease, such as cerebral vascular accident/stroke (< 6 months prior to enrollment), New York Heart Association cardiac disease (Class II or greater), myocardial infarction within the previous 6 months, unstable arrhythmias, or unstable angina
27. Administration of a live/attenuated vaccine within 4 weeks prior to the first dose of study treatment, within 5 months following the administration of the last dose of study drug, or anticipation that such a live/attenuated vaccine will be required during the study
28. Other severe acute or chronic medical conditions including immune colitis, inflammatory bowel disease, immune pneumonitis, pulmonary fibrosis or psychiatric conditions including recent (within the past year) or active suicidal ideation or behavior; or laboratory abnormalities that may increase the risk associated with study participation or study treatment administration or may

interfere with the interpretation of study results and, in the judgment of the investigator, would make the patient inappropriate for entry into this study.

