6.4.1.2 Management of Avelumab Immune-Related Adverse Events

Because inhibition of PD-L1 stimulates the immune system, avelumab may cause toxicity by increasing the immune response, leading to inflammatory reactions collectively referred to as immune-related adverse events (irAEs).

Immune-related adverse events described with this class of drugs include pneumonitis, colitis, hepatitis, endocrinopathies including thyroid disorders (hyperthyroidism, hypothyroidism, thyroiditis), adrenal insufficiency, rash, nephritis and renal dysfunction, eye disorders (including uveitis, iritis), and other immune-mediated reactions including myositis and myocarditis.

Any AE which may have an underlying immune-mediated mechanism including those described above, and without other clear etiologies, should be considered immune-related and managed according to guidelines described in this section.

If a patient has an AE that may be considered immune mediated, treatment for the AE should be administered as if the patient is receiving avelumab.

Treatment of irAEs is mainly dependent upon severity (NCI CTCAE grade):

- Grade 1 or 2: treat symptomatically or with moderate-dose steroids, more frequent monitoring;
- Grade 1 or 2 (persistent): manage similar to high grade AE (Grade 3 to 4);
- Grade 3 or 4: treat with high-dose corticosteroids.

Treatment of irAEs should follow guidelines set forth in [Table 4](#).

Table 4 Management of Avelumab Immune-Related Adverse Events— to be followed only when the Adverse Event is deemed immune related

Gastrointestinal irAEs		
Severity of Diarrhea/Colitis (NCI CTCAE v4)	Initial management	Follow-up management
Grade 1 Diarrhea : <4 stools/day over baseline; Colitis : asymptomatic	Continue avelumab Symptomatic treatment (eg, loperamide)	Close monitoring for worsening Symptoms. Educate patient to report worsening immediately If worsens: Treat as Grade 2 or 3 or 4
Grade 2 Diarrhea : 4 to 6 stools per day over baseline; IV fluids	Withhold avelumab therapy Symptomatic treatment	If improves to Grade 1: Resume avelumab therapy.

indicated <24 hours; not interfering with ADL Colitis : abdominal pain; blood in stool		If persists >5-7 days or recur: Treat as Grade 3 to 4.

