6.8 Prohibited Medications

Patients are prohibited from receiving the following therapies during the screening and treatment phase of this study:

- Antineoplastic systemic chemotherapy or biological therapy
- Immunotherapy not specified in this protocol
- Chemotherapy not specified in this protocol
- Investigational agents other than avelumab and intravesical-BCG
- Systemic glucocorticoids for any purpose other than to modulate symptoms from a suspected immunologic etiology. The use of physiologic doses of corticosteroids may be approved after consultation with the Sponsor. In such cases, systemic steroids should be stopped at least 24 hours prior to the next dose of avelumab.
- **Note:** Inhaled steroids are allowed for the management of asthma.
- Live vaccines within 14 days prior to the first dose of study treatment and while participating in the study. Examples of live vaccines include, but are not limited to, the following: measles, mumps, rubella, chicken pox, yellow fever, and rabies and typhoid (oral) vaccine. Seasonal influenza vaccines for injection are generally killed virus vaccines and are allowed. Intranasal influenza vaccines (eg, Flu-Mist®) are live attenuated vaccines, however, and are not allowed.
- Prophylactic cytokines (G-CSF) should not be administered in the first cycle of the study but may be administered in subsequent cycles according to current ASCO guidelines [32].
- Any surgery that involves tumor lesions. Note: Administration of radiation therapy or surgery done that involves tumor lesions will be considered as disease progression at the time the procedure is performed.

If there is a clinical indication for any medication or vaccination specifically prohibited during the study, discontinuation from study therapy may be required. The Investigator should discuss any questions regarding this with the Sponsor. The final decision on any supportive therapy or vaccination rests with the Investigator and/or the patient's primary physician. The decision to continue the patient on study therapy, however, requires the mutual agreement of the Sponsor-Investigator and the patient.

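### Section 6.8 does not exempt the physiologic-dose corticosteroids that Section 3.2 items 17 and 19b accept at entry, and asks for approved physiologic doses to be stopped 24 hours before avelumab (minor patient-safety inconsistency)

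*Protocol*

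**What the plan says.** **Entry.** Section 3.2 item 17 excludes a history of autoimmune disease but makes an exception for "Patients with medically controlled endocrinopathy (e.g., hypothyroidism, adrenal insufficiency), diabetes type I, vitiligo, psoriasis" and certain thyroid diseases, so controlled adrenal insufficiency is named as acceptable. Item 19 excludes current immunosuppressive medication, and its exception 19b reads "Systemic corticosteroids at physiologic doses", with a limit of 10 mg/day prednisone or equivalent. Neither item requires Sponsor approval, a washout or a change of regimen. SAP Section 4.b, items xvii and xix, repeats both.

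**On study.** Section 6.8 opens with "Patients are prohibited from receiving the following therapies during the screening and treatment phase of this study". Its list includes "Systemic glucocorticoids for any purpose other than to modulate symptoms from a suspected immunologic etiology". It continues "The use of physiologic doses of corticosteroids may be approved after consultation with the Sponsor", followed by "In such cases, systemic steroids should be stopped at least 24 hours prior to the next dose of avelumab". The only steroid it goes on to name as allowed is inhaled steroid for asthma. The closing paragraph says "The final decision on any supportive therapy or vaccination rests with the Investigator" and/or the patient's primary physician. It also says that a clinical need for a prohibited medication may require discontinuation of study therapy, and that continuing needs agreement between the Sponsor-Investigator and the patient.

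**Immune-related events.** Table 4 in Section 6.4.1.2 is "to be followed only when the Adverse Event is deemed immune related". For Grade 1 or 2 endocrinopathy it keeps avelumab going while corticosteroids are started for adrenal insufficiency. For Grade 3 or 4 it allows avelumab to resume whether or not the patient is on hormone replacement. Its rule to discontinue avelumab after more than 12 weeks at 10 mg/day or more of prednisone leaves out hormonal replacement for adrenal insufficiency.

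**The concern.** The entry criteria and the on-study medication rule do not fit together. A patient with controlled adrenal insufficiency enters on a steroid that replaces a missing hormone. From screening onward, 6.8 treats that steroid as prohibited unless the Sponsor approves it, and approval brings an instruction to stop it before avelumab. A site that follows the text withholds essential replacement just before an infusion. A site that continues replacement, which is the safe course, acts against the wording and may have to record a deviation under Section 13.5.

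What is at stake is the safety of an admitted patient and the clarity of the instruction to the site. The sample size, the completion rates and their confidence intervals are not in question.

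**Working it through.** The plan states no figure on this point and no arithmetic applies. The check sets the sections side by side and looks for an exemption elsewhere.

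1. **Who is admitted?** Item 17 admits patients with controlled adrenal insufficiency. Item 19b admits anyone on a physiologic-dose systemic steroid, whatever the reason. If the closing words of item 17 about not requiring immunosuppressive treatment are read as qualifying its whole list, item 19b still accepts the replacement dose up to 10 mg/day.

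2. **How does 6.8 treat them?**

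| Patient at entry | Immunologic-symptom exception in 6.8 | Otherwise |
|---|---|---|
| Autoimmune adrenal insufficiency on replacement | Arguable: replacing a hormone is not plainly modulating symptoms | Approval, then 24-hour stop |
| Non-immune adrenal insufficiency on replacement | Does not apply | Approval, then 24-hour stop |
| Other 19b user | Applies only if the reason is a suspected immunologic symptom | Approval, then 24-hour stop |

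3. **What does the stop attach to?** The sentence before it concerns approved physiologic-dose use. That is the nearest antecedent of the stop, and it describes replacement.

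4. **Is there an exemption elsewhere?**
- Table 4 accepts replacement with avelumab, but its heading restricts it to immune-related adverse events. It does not reach treatment that predates the study.
- Section 3.2 item 11 permits hormone-replacement therapy, but only as an exception to the 3-week washout from anti-cancer therapy.
- Section 6.5 promises supportive measures consistent with optimal care. It is general and names no medication.
- Section 13.5 allows departure without prior IRB approval to remove an immediate hazard. It still requires the departure to be documented as a deviation.
- The discretion clause in 6.8 leaves supportive therapy to the physician, but sits beside the statement that study therapy may have to be discontinued.

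5. **How often would the stop apply?** The text refers to the next dose. That can mean one dose or, on another reading, each dose in turn, with avelumab given weekly during BCG and every two weeks between courses. The documents do not settle which. A once-daily dose could also be moved to after the infusion, so even a repeated stop need not mean a missed day. A count of infusions would therefore not measure harm, and none is used.

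Result: an explicit entry allowance, an on-study prohibition with a stop instruction, and no text that exempts replacement already in use at entry.

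**The case against.** The strongest reply is that nobody applying this protocol sensibly would withdraw adrenal replacement. The stop is advisory (*should*). The physician has the final say on supportive therapy. Section 6.5 calls for optimal supportive care, and Section 13.5 lets a site act at once against an immediate hazard. Sponsor consultation is in-house at a single centre. The stop can also be read as meant for a short course newly requested on study, to end before avelumab resumes, rather than for lifelong replacement.

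Most of this stands. It makes harm unlikely and lowers the weight of the point. It does not remove the inconsistency: each safeguard works by letting the physician set the sentence aside, and none says that replacement in use at entry is permitted. The short-course reading is plausible, but the wording is not limited to new or temporary use.

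A reader might infer more: that the protocol orders replacement to be stopped before every infusion, that admitted patients will be harmed, or that the completion or response endpoints are affected. The documents do not support this. Recurrence is only one reading, the instruction is softened as described, no count of affected patients is given, and nothing links the stop to an endpoint.

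**Conclusion.** The point holds as a minor patient-safety inconsistency between Section 3.2 (items 17 and 19b, repeated in the SAP) and Section 6.8. If followed literally, 6.8 withholds physiologic-dose steroid, including adrenal replacement, from patients the protocol chose to admit. Table 4 shows that the protocol already regards concurrent replacement as acceptable, but does not extend that to patients on replacement at entry.

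The size cannot be stated from the documents: the number of affected patients is unknown and may be zero. No effect on any endpoint or analysis is claimed. The conclusion rests on reading the stop as attached to approved physiologic-dose use, which is the natural reading, and on the immunologic exception not covering all replacement users.

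**What to change.** Add one sentence to Section 6.8:

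> Systemic corticosteroids at physiologic doses already in use at entry as allowed by Section 3.2 items 17 and 19b, and corticosteroid hormone replacement for adrenal insufficiency (present at entry or started under Table 4, at the dose clinically required), are permitted without further approval and are continued without interruption, including on avelumab infusion days; the 24-hour stop does not apply to them.

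This covers every 19b user, not only those on replacement. It sets no 10 mg/day limit on adrenal replacement, because the adrenal entries in Table 4 have none and its 12-week rule leaves such replacement out even at 10 mg/day or more. Physiologic-dose use newly started on study for other reasons still needs Sponsor consultation and stays subject to the stop. Other supraphysiologic use for non-immunologic reasons stays prohibited. Section 3.2, the SAP criteria and Table 4 need no change.

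The cost is one wording amendment with the written IRB approval that Section 13.5 requires, and no new visits, procedures or patients. The clinical downside is that these patients receive avelumab alongside a low steroid dose, which the protocol already accepts at entry or under Table 4.

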4 PATIENTS REGISTRATION

4.1 Required Protocol Specific Regulatory Documents

This protocol, the Informed Consent document, any information to be given to the patient, and relevant supporting information must be submitted to the IRB by the Principal Investigator and reviewed and approved by the IRB before the study is initiated.

4.2 Patients Registration and Enrollment

Patients must have signed and dated all applicable consents and authorization forms to be registered in the Velos eResearch database system, which is sponsored by The University of Oklahoma Stephenson Cancer Center (OU-SCC).

A Screening identification (Screening ID) number will be provided by OU-SCC research staff. After all screening procedures and assessments have been completed and eligibility has been established, the subject Study ID number will be generated by OU-SCC. Once the patient has been provided a Study ID number, only the Study ID number should be used. Both patient ID numbers should be documented in Velos.

Patients must not start protocol treatment prior to registration and enrollment. A patient will start protocol treatment only after the pre-treatment evaluation is complete and eligibility criteria have been met.

[figure not shown]
NOTE: Per the Institutional Review Board (IRB) reporting, a patient is considered accrued once he or she signs a consent form for the study. A patient is considered enrolled once the patient begins treatment. Evaluable patients are defined in protocol Section 8.2.1.

5 STUDY DESIGN

5.1 Study Timeline

Study timeline is summarized in Figure 1 Schema.

Figure 1 Schema

5.2 Overall Study Design

This is an open-label phase Ib trial of avelumab and intravesical BCG in patients with NMIBC. The study will utilize a modified 3+3 design for potential dose de-escalation in case of patients cannot tolerate to a full dose intravesical BCG. In order to adequately assess safety data at the conclusion of this combination therapy, 3~6 patients will be enrolled at starting dose level (dose level 1). Dose limiting toxicity will be based on the first 6 weeks of proposed study treatment. If 0/3 patients experience a DLT, dose expansion cohort will be activated for additional 15 patients. If 1/3 patients experiences a DLT, the dose level 1 will be expanded to 3 more patients. If 1/6 patients experiences a DLT, the dose expansion cohort will be activated for additional 12 patients. If 2 or more of the 6 patients experience a DLT, the dose level -1 will be evaluated.

At the dose level 1, 3~6 patients will be enrolled to evaluate the safety of proposed combination therapy with standard BCG dosing (50 mg) plus avelumab (10 mg/kg, IV weekly during BCG and every two weeks between BCG). The ability of patients to receive a complete induction course of combination therapy is defined as 5 of 6 weekly treatments of BCG with weekly infusion of avelumab within an 8 week period. Patients will continue maintenance therapy if they tolerate the induction course. Eligible patients will receive avelumab 10 mg/kg, IV weekly dosing plus intravesical BCG 50 mg weekly, 6 weeks on, then 6 weeks off during induction and will continue on a standard maintenance regimen with combination therapy for 1 year. Maintenance therapy beyond 1 year will be at the discretion of the treating physician and will be BCG monotherapy.

The dose limiting toxicity (DLT) period is weeks 1-6 (42 days). If the combination therapy in dose level 1 is well tolerated (0/3 or 1/6 patients experience a DLT), additional 12~15 patients with the same eligibility criteria will be enrolled at dose level 1 for a total of 18 patients in a dose expansion study. If the combination therapy in dose level 1 is not tolerated (2 or more patients experience a DLT), dose level -1 (avelumab 10mg/kg and BCG 33mg) will be evaluated in 3~6 eligible patients. If the combination therapy in dose level -1 is well tolerated (0/3 or 1/6 patients experience a DLT), additional 12~15 patients with the same eligibility criteria will be enrolled at dose level -1 for a dose expansion study. If the combination therapy in Cohort -1 is not tolerated (2 or more patients experience a DLT), the study will be suspended for reassessment.

5.2.1 Definition of Dose limiting toxicity

During safety lead-in phase, Dose limiting toxicity (DLT) will be monitored during the first 6 weeks of the combination avelumab and intravesical BCG. DLTs will be defined as any and all adverse events at least possibly related to study drug which occur in the DLT evaluation period and meet the criteria below, as evaluated by the NCI-CTCAE version 5.0.

Note: DLTs and other toxicities will be discussed between the Principal Investigator, and the Data Safety Monitoring Committee (DSMC). The discussions are the basis for the decisions regarding dose expansion (or de-escalation) according to the rules of the protocol.

DLT will be classified as either hematologic or non-hematologic toxicity (assessed in accordance with the CTCAE Version 5.0 criteria).

The following are DLTs:

1. Toxicity causing greater than 2 weeks of dose delay. For example, if a subject has dose delay greater than 2 weeks due to an AE, such AE is a DLT.
2. Grade 4 neutropenia greater than 5 days.
3. ALT/AST $> 3x$ ULN with bilirubin $> 2x$ ULN without another explanation (e.g., cholestasis)
4. Any Grade 3 hypersensitivity reaction is a DLT
5. Grade 4 thrombocytopenia of any duration
6. Grade 3 thrombocytopenia with significant hemorrhage of any duration
7. Febrile neutropenia

And, any non-hematological Grade ≥ 3 toxicities will be a DLT.

The following may be considered as exceptions to DLTs:

1. Grade 3 nausea, vomiting, or diarrhea and Grade 4 vomiting or diarrhea in the absence of maximal medical therapy that resolves in 72 hours
2. Grade 3 fatigue lasting < 5 days
3. Grade 3 hypertension that can be controlled with medical therapy
4. An increase of indirect (unconjugated) bilirubin indicative of Gilbert's syndrome
5. Serum lipase and/or serum amylase CTCAE Grade 3 ≤ 7 consecutive days without clinical signs or symptoms of pancreatitis

5.2.1.1 Definition of DLT Evaluable Population:

Patients enrolled in safety lead-in cohort who receive at least 4 doses and complete the DLT observation period (the first 42 days of induction treatment), unless the patient discontinued the study treatment due to a DLT.

